Statistical Considerations:	
Sample size according to experience and to established specialized literature.
 
Descriptive statistics: Frequency distribution, mean and standard deviation, median and quartile, boxplot, histogram, scatterplot.
 
Inferential statistics: t-Test, Mann-Whitney-U-Test, Wilcoxon-Test, correlation coefficient (Pearson, Spearman) .

GCP Statement:	
This study will be conducted in compliance with the protocol, the current version of the Declaration of Helsinki, the ICH-GCP or ISO EN 14155 (as far as applicable) as well as all national legal and regulatory requirements.

STUDY SUMMARY IN LOCAL LANGUAGE

In dieser Studienreihe findet eine methodische klinische Evaluation von neuen CE-zertifizierter Phonak Hörsystemen zur Qualitätskontrolle vor dem jeweiligen Produktlaunch statt. Das Ziel der Untersuchungen ist es, mithilfe von hörgeschädigten Studienteilnehmern, eine fehlerfreie Leistungsfähigkeit des gesamten Phonak Hörsystems zu gewährleisten. Das Phonak Hörsystem umfasst Hörgeräte unterschiedlicher Formfaktoren, akustische Ankopplung, drahtloses Zubehör (z.B. Fernbedienung) sowie die Anpass-Software. Des Weiteren wird die Sicherstellung des maximalen Nutzens für den Träger des Hörsystems anhand von objektiven Labormessungen sowie von subjektiven Bewertungen beim Tragen im Alltag angestrebt. Im Zuge dieser Untersuchungen werden die neu entwickelten Phonak Produkte mit ihren Vorgängermodellen sowie mit Mitbewerberprodukten verglichen. Diese klinische einfachblinde Studienserie erfolgt unter kontrollierten, randomisierten Bedingungen am Hauptsitz der Sonova AG in Stäfa.

ABBREVIATIONS

Provide a list of abbreviations used on the protocol - to be completed

AE	Adverse Event
ANL	Acceptable Noise Level
BTE	Behind-The-Ear device
CA	Competent Authority (e.g. Swissmedic)
CEC	Competent Ethics Committee
CRF	Case Report Form
CU	Categorical Unit
ClinO	Ordinance on Clinical Trials in Human Research (in German: KlinV, in French: OClin)
CTCAE	Common terminology criteria for adverse events
dB	Decibel
DD	Device Deficiencies
DM	Digital Modulation
DSUR	Development safety update report
eCRF	Electronic Case Report Form
pCRF	Paper Case Report Form
FM	Frequency Modulation
GCP	Good Clinical Practice
GöSa	Göttinger Satztest
IB	Investigator's Brochure
ITE	In-The-Ear device
Ho	Null hypothesis
H1	Alternative hypothesis
HFG	Humanforschungsgesetz (Law on human research)
HIBAN	Hearing Instrument Body Area Network
HMG	Heilmittelgesetz

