4.2 Primary Objective

The study seeks primarily to grant zero-defect overall performance of the new Phonak Hearing Systems.

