5.2 Secondary Outcomes

Product benchmark: Comparison of new Phonak Hearing Systems to previous models and to competitor devices according to primary objectives in accordance to table 4.

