6.1 General study design and justification of design

(ICH/E6 6.4.2, 6.4.5; AGEK 4.2; SPIRIT #8)

ICH: The scientific integrity of the trial and the credibility of the data from the trial depend substantially on the trial design.

ICH: A description of the type/design of trial to be conducted (e.g., double-blind, placebo-controlled, parallel design) and a schematic diagram of trial design, procedures and stages.

ICH: The expected duration of subject participation, and a description of the sequence and duration of all trial periods, including follow-up, if any.

A methodical evaluation of new CE-Labelled Phonak Hearing Systems is intended to be conducted on hard of hearing participants to grant quality control prior to product launch in spring or in fall per year. The aim of the investigation is to continuously ensure zero-defect overall performance of the new hearing systems as well as maximum benefit for the participant with the devices in comparison to previously outstanding Phonak Hearing Systems and to equivalent strong competitor devices across 10 years (October 2015 to 2025). This will be a controlled, single blinded (participants), randomised (testing method), cross-over (investigational product) active comparator study which will be conducted mono centric at Sonova AG Headquarters based in Stäfa.

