11.1 Hypothesis

This is a methodical evaluation in which new hardware and software technologies of Phonak products shall be compared with previous outstanding Phonak Hearing Systems and with equivalent competitor devices regarding a zero-defect overall performance and a maximum audiological benefit for the user. Hence, this study will not test a specific hypothesis.

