11.2 Determination of Sample Size

ICH: The number of subjects planned to be enrolled. In multicentre trials, the numbers of enrolled subjects projected for each trial site should be specified. Reason for choice of sample size, including reflections on (or calculations of) the power of the trial and clinical justification.

Based on numerous publications in the field of audiology research using standardized measurement methods testing hearing impaired subjects as well as on Sonova AG's extensive study experience, a number of maximum 20 subjects per study is sufficient to obtain statistically significant results on a significance level of 5%.

In the case of the pre-study a maximum of 5 subjects is included, since merely the study concept needs to be proved, and no inferential but only descriptive statistics is carried out. Later, during the main study, both descriptive and inferential statistics are executed. In the past, typically 20 subjects participated per study leading to significant results approaching the primary objective (zero-defect overall performance of the new Phonak Hearing Systems). To tackle the secondary objective (product benchmark) a number up to 30 subjects have taken part in several previous investigations. This case is founded in the fact that a study design of parallel groups, either containing 10 or 15 subjects each, is applied as soon as more than one competitor device is compared to the Phonak Hearing System. For this reason, an appropriate number of subjects will be included during the planned investigations.

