11.4 Planned Analyses

ICH: A description of the statistical methods to be employed, including timing of any planned interim analysis(es).

In a first step, the distribution of the collected subjective and objective data is verified. Based on this outcome (normally distributed yes/no) and depending on the scale level (nominal, ordinal, interval or rational) of the variables, descriptive statistics is executed in the form of determining the mean value and standard deviation or the median and quartile, respectively. Furthermore, diagrams for visualization are compiled such as boxplots, histograms and scatterplots. Then, after a determination of the measurement variables regarding their relationship or their difference, inference statistics is executed by applying the appropriate parametric or non-parametric test depending on the data's distribution either using the correlation coefficient (Pearson, Spearman), t-Test, Mann-Whitney-U-Test, or the Wilcoxon-Test. Generally, a significance level of 5% is pursued.

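### Section 11.2 supports its 20 subjects with alpha alone, and the analyses in 11.4 neither bound the malfunction rate nor show how uncertain a benchmark difference is

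*Combined protocol and SAP*

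**What the plan says.** Section 11.2 introduces its figure by pointing to published audiology research and to the sponsor's own studies, then says "a number of maximum 20 subjects per study is sufficient to obtain statistically significant results on a significance level of 5"%. The synopsis gives the same basis: "Sample size according to experience and to established specialized literature". No source is tied to a particular effect, SD or power, and section 11.1 adds "Hence, this study will not test a specific hypothesis".

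The second paragraph of 11.2 treats the benchmark separately. Up to 30 subjects have been used, because a "study design of parallel groups, either containing 10 or 15 subjects each, is applied as soon as more than one competitor device" enters the comparison. The synopsis and section 6.1 cap a main study at 30. Section 6.1 describes a "cross-over (investigational product) active comparator study".

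The primary objective in section 4.2 is absolute: "The study seeks primarily to grant zero-defect overall performance of the new Phonak Hearing Systems". In Table 4 (section 5.1), system stability and audible malfunctions are recorded as yes/no and open-ended replies. The secondary outcome in section 5.2 is "Comparison of new Phonak Hearing Systems to previous models and to competitor devices according to primary objectives".

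For analysis, section 11.4 lists means with SDs or medians with quartiles, plots, correlation coefficients, and t, Mann-Whitney or Wilcoxon tests: "Generally, a significance level of 5% is pursued". The synopsis adds frequency distributions. Confidence intervals appear in neither place. Section 6.1 notes that devices may be revised during a study, so that firmware versions differ and have to be taken into account in the analysis. Section 13 allows results to support product claims.

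**The concern.** A significance level does not fix a sample size. Whether 20 subjects suffice depends on the difference sought, its variability and the power wanted, and none of these is given. A reader of 11.2 cannot tell which differences a study of this size would probably miss.

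The larger gap is in 11.4. The zero-defect objective concerns how rarely something goes wrong, and none of the listed tests or correlations puts an upper bound on a malfunction rate. Frequency tables would show a count of zero, but not how high a rate that count leaves open. For the benchmark, a p-value without an interval does not show how large a difference remains compatible with the data. Both results may go into brochures for professionals and users, so their uncertainty should be visible.

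**Working it through.** **Inputs from the documents.** Alpha 5% (11.2, 11.4); 20 subjects (11.2); cap of 30 per main study (synopsis, 6.1); parallel groups of 10 or 15 when more than one competitor is compared (11.2); cross-over of products (6.1); yes/no malfunction items (Table 4).

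**Assumed, because not stated.** t-test, two-sided, 80% power, no multiplicity adjustment. Results are in SD units because no SD is given.

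**1. Can 20 be reproduced?** No. For paired data, n ≈ ((z for alpha + z for power)/d)², where d is the difference in SDs of the within-person difference. With alpha alone, d and power are both free. By the normal approximation, n = 20 matches d = (1.960 + 0.842)/√20 = 0.63 at 80% power, or (1.960 + 1.282)/√20 = 0.73 at 90%. Any n would match some d.

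**2. What no reported malfunction shows.** With one yes/no per subject, independent subjects and one fixed version, the exact one-sided upper 95% limit for zero events is 1 − 0.05^(1/n).

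- 0/20: 13.9%
- 0/30: 9.5%
- If only 15 or 10 subjects used a given firmware version (illustration): 18.1% or 25.9%

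The chance of seeing no malfunction at an assumed true rate of 5% is 0.95^20 = 36% or 0.95^30 = 21%. At an assumed 10% it is 0.90^20 = 12% or 0.90^30 = 4%.

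**3. Which benchmark designs fit the cap.** Parallel groups apply only with more than one competitor. A between-group comparison of Phonak with two competitors needs at least three arms: 3 × 10 = 30 fits, but 3 × 15 = 45 does not. Groups of 15 fit as 2 × 15 = 30 if each group compares Phonak with one competitor within person. Groups of 10 could be used either way, and 11.2 does not say which.

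**4. Detectable differences.** Power comes from the noncentral t distribution. Paired: df = n − 1, noncentrality d√n. Two groups of n: df = 2n − 2, noncentrality d√(n/2). The range column runs from one-sided 5% with 80% power to two-sided 5% with 90% power.

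| Design | Detectable, two-sided 5%, 80% power | Range | Power at 0.5 SD / 0.8 SD (assumed) |
|---|---|---|---|
| Cross-over, 20 | 0.66 SD of difference | 0.58–0.76 | 56.5% / 92.4% |
| Cross-over, 30 | 0.53 SD of difference | 0.47–0.61 | 75.4% / 98.8% |
| Paired within group of 10 | 1.00 SD of difference | 0.85–1.16 | 29.3% / 61.6% |
| Paired within group of 15 | 0.78 SD of difference | 0.68–0.90 | 43.8% / 82.1% |
| Between groups of 10 (three arms) | 1.32 between-subject SD | 1.16–1.53 | 18.5% / 39.5% |

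At a true 0.5 SD, the test is therefore non-significant in 100 − 56.5 = 43.5% of cross-over comparisons of 20 and in 100 − 18.5 = 81.5% of comparisons between groups of 10.

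The two SD scales are not interchangeable. One SD of the difference equals √(2(1 − ρ)) between-subject SDs, where ρ is the within-person correlation. So 0.66 SD of the difference is 0.93, 0.66 or 0.42 between-subject SD at ρ = 0, 0.5 or 0.8; ρ is not stated.

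**5. What an interval would show.** The half-width of the 95% interval is t/√n = 2.093/√20 = 0.47 SD of the difference for a cross-over of 20, and t√(2/n) = 2.101 × √0.2 = 0.94 SD between groups of 10.

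**The case against.** The strongest reply is that this is a quality evaluation that disclaims a specific hypothesis, so no formal power calculation is required, and that the figure is not a bare assertion: 11.2 cites literature and past studies. That stands as far as it goes. The publications and past data cannot be seen, and 20 subjects in a cross-over give 92.4% power at 0.8 SD. A reader might infer that 20 is too few or that the plan has miscalculated, but the documents do not support this. They give no effect against which 20 could fail. Nor does the cited experience supply the missing inputs: Table 2 lists past objectives and sizes, but no results or SDs.

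A reader might also infer that the sponsor will take a non-significant benchmark as equality, or silence on malfunctions as proof of none. No passage says so. The point is only that the planned output would not guard against either reading.

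A third tempting step is to quote a detectable difference between two groups of 15. Under the cap and the more-than-one-competitor condition, that is not an available Phonak-versus-competitor comparison.

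Finally, the binomial limit simplifies what is done. Deficiencies are captured at every visit, replies can be open-ended, and devices are corrected during the study. That is fair: the limit summarises the yes/no items and does not replace the deficiency record. Counting devices does not remove the issue either. If both ears were fitted and devices were independent (assumptions), 0/40 and 0/60 give 1 − 0.05^(1/40) = 7.2% and 1 − 0.05^(1/60) = 4.9%. Section 6.1 already says firmware must be considered, but gives no method.

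**Conclusion.** The sufficiency statement in 11.2 is unsupported, not shown to be wrong; taken alone, it is a missing justification. The more useful finding is that 11.4 has no output that bounds the malfunction rate or shows the uncertainty of a benchmark difference.

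A clean result leaves a per-subject malfunction rate of up to 13.9% (20 subjects) or 9.5% (30) open. Detectable benchmark differences run from 0.53 SD of the within-person difference (cross-over of 30) to 1.32 between-subject SD (groups of 10). The malfunction limits assume one reply per subject, independent subjects and one fixed version. The detectable differences assume a two-sided 5% t-test, 80% power and no multiplicity adjustment. The miss rates also depend on the assumed 0.5 SD. This should be corrected, and it can be done without changing the study's size.

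**What to change.** In order of value:

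1. **Section 11.4, malfunction items (the main change).** For each yes/no item, report the number of subjects with at least one malfunction and the exact one-sided upper 95% limit (0/20: 13.9%; 0/30: 9.5%), stating that this takes one reply per subject and independent subjects. Where devices were revised during the study, give both by firmware version, with the subjects who used that version as denominator.
2. **Section 11.4, benchmark.** Report each comparison as an estimated difference with a 95% confidence interval, using the Hodges-Lehmann estimate and interval where a Wilcoxon or Mann-Whitney test is used. State that non-significance is not evidence of equality.
3. **Section 11.2.** Replace the sufficiency statement with the detectable difference for the design in use, labelled as assuming a two-sided 5% t-test, 80% power and no multiplicity adjustment. Cross-over: 0.66 (n = 20) or 0.53 (n = 30) SD of the within-person difference. Paired within a group of 10 or 15: 1.00 or 0.78 SD of the difference. Between groups of 10 (three arms): 1.32 between-subject SD. Say which benchmark comparison applies.

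Cost: one statement replaced and a few sentences added, with no extra subjects, visits or measurements. The stated adequacy will look less favourable, limits by firmware version will be wide, and there is slightly more to report.

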11.3 Statistical criteria of termination of trial

ICH: A description of the "stopping rules" or "discontinuation criteria" for individual participants, parts of trial and entire trial.

After each pre-study an analysis is performed. The corresponding results are the basis for the further progress of the main study which might be adjusted accordingly, if necessary.

11.4 Planned Analyses

ICH: A description of the statistical methods to be employed, including timing of any planned interim analysis(es).

In a first step, the distribution of the collected subjective and objective data is verified. Based on this outcome (normally distributed yes/no) and depending on the scale level (nominal, ordinal, interval or rational) of the variables, descriptive statistics is executed in the form of determining the mean value and standard deviation or the median and quartile, respectively. Furthermore, diagrams for visualization are compiled such as boxplots, histograms and scatterplots. Then, after a determination of the measurement variables regarding their relationship or their difference, inference statistics is executed by applying the appropriate parametric or non-parametric test depending on the data's distribution either using the correlation coefficient (Pearson, Spearman), t-Test, Mann-Whitney-U-Test, or the Wilcoxon-Test. Generally, a significance level of 5% is pursued.

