Background and Rationale:	Phonak Hearing Systems pass through different development and study stages. At an early stage, feasibility studies are conducted to investigate new algorithms, features and functions in an isolated manner. If the benefit is proven, their performance is then investigated regarding interdependency between all available algorithms, features and functions running in parallel in a hearing aid (pivotal/pre-validation studies) and, as a result, they get optimized. Afterwards, and prior to product launch, the Phonak Hearing Systems undergo a final quality control in terms of clinical trials in the way as planned for this study (“phase of final inspection”).
Primary Objective(s):	Zero-defect overall performance of the new Phonak Hearing Systems: 
 • Technical: Sound quality, system stability and no distortions/artefacts/interruptions/feedback/system noise or other malfunctions occur. • Audiological: In the lab (objective: Standardised speech intelligibility measures in quiet/noise, threshold measures, cognitive measures, simulations of various listening situations, interviews) and in the users’ everyday life (subjective: questionnaires). • Handling: Rate of applicability, size, robustness, look-and-feel.
Secondary Objective:	Product benchmark: Comparison of new Phonak Hearing Systems to previous outstanding Phonak models and to competitor devices according to primary objectives.
Outcome(s):	
 • Lab trials: Objective and subjective test results • Home trials: Subjective test results
Study design:	Active comparator study, controlled, single blinded, randomised, cross-over or parallel design.

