7.2 Recruitment and screening

(ClinO, Art 25, Appendix 3, 1.4 & 1.6; AGEK 5.1; SPIRIT #15)

At Sonova AG Headquarters, a subject database is existing which is currently containing approx. 1000 hearing impaired subjects (various degrees of hearing loss) from circumjacent cantons. Furthermore, this database is containing hearing impaired employees from Sonova AG (internal subjects). The database is permanently extended (study independently) with new subjects recruited via different paths and screened by qualified Audiologists employed at Sonova AG:

- Phonak homepage (status 22.11.2019): <https://www.phonak.com/ch/de/hoerverlust/feldstudie-anmeldung.html>
- Flyer Phonak Feldstudien (see attachment: 4b1_Flyer_Phonak_Feldstudien.pdf)
- Campaign "Probanden werben Probanden" (see attachment: 4b2_Kampagne_Probanden_werben_Probanden.pdf)
- Advertisement in magazine Decibel (see attachment: 4b3_Inserat_Decibel.pdf)
- Links at homepages from organization of hearing impaireds, e.g.:
 - o ProAudito (status 19.05.2015): http://www.proaudito-zuerich.ch/fileadmin/customer/Medien/Home_und_Aktuell/pdf/Inserat_Phonak_sucht_Probanden.pdf
 - o Audiopädagogik.ch (status 19.05.2015): <http://www.audiopädagogik.ch/phonak-sucht-probanden-ab-sofort/>

After the study approval by the CEC and after a subsequent successful Initiation Visit undertaken by the monitor, the subject recruiting by contacting potential candidates can be started. At this initial contact, the time expenditure and the availability period will be discussed in advance. In case of a positive reply, the participant information as well as the informed consent form is sent to the potential study participant by post or email one week prior to the screening appointment, at least, and the subject is invited via telephone or email for an assessment of his hearing at Phonak HQ. The audiological history of a subject and a pure tone audiogram as well as a speech audiogram is recorded, the inclusion and exclusion criteria are requested and open questions concerning the study itself, the participant information and the informed consent form are replied before the decision about a study participation is made and the signed document is collected by the investigator. If a participant quotes hearing a tinnitus, a Tinnitus Pitch and Loudness Matching is executed to determine its frequency and intensity (section 5.1, table 4).

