9.3.1 Screening appointment

- Mapping to an encoded and randomized subject ID
- Discussion of the subject information and signing of the informed consent which were sent in advance by post or email
- Recording of the subject's audiological history
- Ear and ear canal assessment (otoscopy)
- Hearing test (pure tone and speech audiometry)
- In case of tinnitus: Tinnitus Pitch and Loudness Matching
- Explanation of in-/exclusion criteria
- Decision if patient can participate in the trial regarding to the in-/exclusion criteria
- eCRF Screening
- eCRF Audiometry
- Scheduling of the next visit

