11.4.3 Secondary Analyses

The secondary analysis is done in the same way as the primary analysis.

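### Section 11.4 specifies no baseline-adjusted or period-adjusted device contrast, although the screening audiogram and device order are held; if devices are truly randomised this costs power, not overall type I error

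*Combined protocol and SAP*

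**What the plan says.** Section 11.4 first checks the distribution and scale level of each variable. It then chooses a test, "either using the correlation coefficient (Pearson, Spearman), t-Test, Mann-Whitney-U-Test, or the Wilcoxon-Test", at a 5% level. The synopsis repeats the list: "Inferential statistics: t-Test, Mann-Whitney-U-Test, Wilcoxon-Test, correlation coefficient". For the product benchmark, 11.4.3 adds only this: "The secondary analysis is done in the same way as the primary analysis". Neither place names a covariate, a period or a sequence term. Hearing loss enters the analysis only through the severity subgroups of 11.4.1.

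The data needed for adjustment exist. At screening, "a pure tone audiogram as well as a speech audiogram is recorded" (section 7.2; 9.3.1 agrees). Section 6.2.1 applies randomisation to all investigational products, and 6.3 notes that the lists identify each person's measurement order.

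The design is described in three ways. The synopsis has "randomised, cross-over or parallel design". Section 6.1 has "cross-over (investigational product) active comparator study". Section 11.2 adds a "study design of parallel groups, either containing 10 or 15 subjects each" when more than one competitor is compared with the Phonak system. On allocation, 6.1 attaches randomisation to the testing method, 6.2.1 attaches it to the products, and 7.3 says assignment is by chance but explains this as taking the first eligible people who agree.

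**The concern.** The studies are small (20, or up to 30 for the benchmark), and section 13 allows results to support product claims. Two sources of variation may stay in the error term without need.

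- **Between parallel groups.** Section 6.1 foresees losses from mild to profound, depending on form factor. Where an outcome such as a speech test tracks hearing loss, differences between people inflate the error of an unadjusted comparison.
- **Within person.** In a cross-over, a shift between periods (practice, acclimatisation) adds to the spread of the paired differences.

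Adjustment would use data already collected. Section 11.1 tests no specific hypothesis and the plan sets no power target, so what is at stake is the width of intervals and the chance of missing a real device difference.

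**Working it through.** **Inputs from the documents.** Level 5% (11.4; taken as two-sided); 20 people per study, or groups of 10 or 15 (11.2). The documents give no effect size, SD, correlation, period shift or power. Every value of those below is an assumption, and 80% power is a benchmark chosen for this review.

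**The plan's own figure.** Section 11.2 calls 20 people sufficient for significance at 5%. Without an effect size this cannot be reproduced, only inverted. By the noncentral t distribution, a paired test with n = 20 has 80% power at 0.66 SD of the within-person difference and 90% at 0.76 SD. Parallel groups need 1.06 SD (15 per group) or 1.32 SD (10 per group) for 80%.

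**(a) Contrast between two parallel groups of m people.** Unadjusted noncentrality is d·√(m/2): 1.060 × √7.5 = 2.90 for m = 15, and 1.325 × √5 = 2.96 for m = 10. ANCOVA with a covariate of correlation r divides this by √[(1 − r²)(1 + F/(2m − 2))], where F follows F(1, 2m − 2) and allows for chance imbalance; df = 2m − 3.

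| r | m = 15 | m = 10 |
|---|---|---|
| unadjusted | 80% | 80% |
| 0 | 78% | 77% |
| 0.3 | 82% | 81% |
| 0.5 | 89% | 88% |
| 0.7 | 97% | 97% |

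Break-even is r ≈ 0.20 (m = 15) and 0.25 (m = 10). If recruitment by form factor halves the spread of hearing loss, r becomes 0.5r/√(1 − r² + 0.25r²). Correlations of 0.3, 0.5 and 0.7 then fall to 0.16, 0.28 and 0.44, and power is 79, 82 and 86% (m = 15) or 78, 81 and 86% (m = 10).

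This part does not carry over to within-person contrasts. Pairing removes a stable audiogram effect: with a very large simulated one, paired power stayed at 80%.

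**(b) Two-period cross-over, n = 20, effect 0.66 SD.** The paired difference is modelled as effect ± shift + error (SD 1), with the sign set by order. With balanced orders a shift of 0.5 raises the expected sample variance to 1 + 0.25 × 20/19 = 1.263. Noncentrality then falls from 0.66 × √20 = 2.95 to about 2.95/1.124 = 2.63. The period-adjusted test is a two-sample t test of period differences between order groups. Simulated power:

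| Shift (SD) | Balanced, unadjusted | Balanced, adjusted | Coin-flip, unadjusted | Coin-flip, adjusted |
|---|---|---|---|---|
| 0 | 80% | 80% | 80% | 77.5% |
| 0.25 | 78% | 80% | 77.5% | 77.5% |
| 0.5 | 72% | 80% | 71% | 77.5% |
| 1.0 | 49% | 80% | 50% | 77.5% |

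With no shift, the adjusted test costs about 1 point at n = 10 with balanced orders (80.0% to 78.7%), against about 6 points with coin-flip order.

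**(c) Type I error of the listed tests, unadjusted.**

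- Randomised parallel groups: t 4.9 to 5.2%, Mann-Whitney 4.1 to 4.7%.
- Coin-flip order: paired t about 5% at every shift.
- Balanced orders: 5.0, 2.9 and 0.6% at shifts of 0, 0.5 and 1 SD, so conservative.
- Conditional on an uneven split of orders, the unadjusted estimate is biased by shift × (difference in order counts)/n. At 14:6 with a 0.25 SD shift the bias is 0.25 × 8/20 = 0.10 SD, and the error is about 6.5%. At 8:2 (n = 10) with 0.4 SD the bias is 0.24 SD, and the error is about 8.8%. The adjusted test stays at 5%. Splits at least that uneven occur in 11.5% and 10.9% of coin-flip trials.
- Parallel groups that differ systematically by 0.5 SD in audiogram, because they were not randomised: 8 to 15% (10 per group) or 10 to 21% (15 per group) for audiogram R² of 0.25 to 0.75.

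**The case against.** **The tests can adjust.** A reader might infer that the listed tests rule out any adjustment. They do not. A t or Mann-Whitney test of period differences between order groups is the usual two-period analysis, and 11.4.1 allows contrasts within hearing-loss strata. What stands is that the plan does not specify the period analysis, and that four severity bands in 20 to 30 people are a poor substitute for a covariate.

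**Type I error.** A reader might also infer that false positives are inflated. Under randomisation they are not, overall. Nor do the documents show that groups are formed first-come: 7.3 may describe enrolment only, and 6.2.1 says products are randomised. But the three sections do not agree, so the reassurance is conditional.

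**Part (a) may rarely apply.** The groups of 11.2 may each compare Phonak with one competitor within person, and then no audiogram covariate is needed. Devices are also fitted to the individual loss (3.2), which may weaken the correlation. Both points stand and limit the covariate advice.

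**Part (b) is a simplification.** The main study has ten study visits, and rapid-switching tasks such as paired comparison or MUSHRA may have no device periods. Training sessions (9.2) and randomised order (6.2) already limit shifts. A period term would not in general capture the firmware changes that 6.1 says the analysis must consider. This stands, and the advice is confined to contrasts with distinct device periods.

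**Conclusion.** The point holds as an efficiency matter: the plan leaves baseline and period adjustment unspecified although the data are in hand. No stated figure is wrong. The gain ranges from nothing (covariate correlation below about 0.20 to 0.25, or no period shift) to 9 points of power at r = 0.5 with 15 per group and 8 points at a 0.5 SD shift with balanced orders. These sizes rest wholly on assumed correlations and shifts, and the covariate part applies only to contrasts between parallel groups. The statement that overall type I error is kept rests on real randomisation of devices or their order, which 6.1, 6.2.1 and 7.3 do not state consistently; first-come formation of parallel groups would risk bias. Yes/No malfunction outcomes are outside this point. It is worth considering, with medium confidence.

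**What to change.** 1. **Sections 6.1, 6.2.1 and 7.3:** reconcile them, so that it is plain that devices, device orders and any parallel groups are allocated at random and that first-come applies to enrolment only, if that is the intention.
2. **Section 11.4, parallel groups:** state for each benchmark contrast whether it is between or within persons. Where it is between groups, use ANCOVA with device group and one covariate named in advance: the screening pure-tone average, or the screening speech score for speech tests. Limit this to outcomes expected to track hearing loss, and use a rank or proportional-odds version for ordinal ratings.
3. **Sections 6.2.1 and 11.4, cross-over:** state that the script generates balanced device orders, and analyse contrasts with distinct device periods with a period term. For two periods, the two-sample test of period differences between order groups is enough. Keep the term if dropouts leave the orders uneven, since that is where the unadjusted test loses its conditional error control.

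Cost: wording, a small change to the script and slightly more analysis work, with no new data. The covariate loses at most 2 to 3 points of power if its correlation is below about 0.20 to 0.25. The period term with balanced orders loses under 1 point at n = 20 and about 1 point at n = 10 when there is no shift.
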